8.3.1.1. Sensitivity Analysis of Annualized Rate of Change (Slope) in eGFR

Two sensitivity analyses will be performed on the annualized rate of change (slope) in eGFR (2021 CKD-EPIcr_R) using the PPAS and SEAS.

The sensitivity analysis using the PPAS is the same as the primary analysis for the annualized rate of change (slope) in eGFR on treatment (Section 8.3.1) but using PPAS.

The sensitivity analysis using the SEAS will use the change from baseline in eGFR values assessed at the end of lixivaptan titration, on-treatment eGFR values assessed during the Doubleblind, Randomized Treatment visits and off-treatment eGFR values assessed during the Followup Period I visits. Note that on-treatment eGFR values obtained 1 days after the latest dose and off-treatment eGFR values obtained prior to 8 days after the last dose will be excluded in the analysis. An acute hemodynamic effect will be considered for eGFR at the end of lixivaptan titration for all the participants and for all eGFRs on treatment for the lixivaptan participants. All other eGFRs will not be considered for the hemodynamic effect. The acute hemodynamic effect indicator/flag (ACUHEMO) will be included in the model (1=Yes) or (0=No).

The linear mixed effect model with effects of time (as a continuous variable in years), treatment, time-by-treatment interaction, acute hemodynamic effect, baseline (of the primary endpoint), and randomization stratification factors (CKD stage [CKD2 versus CKD3/4] and Mayo Clinic ADPKD Image Classification [1C, 1D, or 1E]) will be used to fit the GFR estimates, in which the intercept and time are both a fixed effect and a random effect. An unstructured variance-covariance matrix is assumed for the modeling.

Example SAS code is shown below:

```
PROC MIXED EMPIRICAL;
```

```
CLASS TREATMENT ACUHEMO CKD_STAGE MAYO_CLASS USUBJID;
MODEL CHG_eGFR = TREATMENT ACUHEMO BASELINE TIME TIME*TREATMENT CKD_STAGE
MAYO_CLASS /SOLUTION;
RANDOM INTERCEPT TIME/TYPE=UN SUB= USUBJID;
ESTIMATE "Annualized Slope of On-Treatment eGFR" TIME*TREATMENT -1 1;
```

RUN;

The estimate of the treatment group by visit interaction will be used for this analysis.

8.3.2. Annualized Percent Change from Baseline in htTKV

The 2nd secondary efficacy endpoint is the annualized percent change in htTKV from baseline to 28 days after the last dose of the study drug, i.e., Visit 25 during the Follow-up Period I after Week 52 for on-treatment completers or, for participants who discontinue study drug treatment prior to Week 52 [Visit 22], during the Follow-up Period 28 days following study drug treatment discontinuation. Baseline htTKV is the one obtained at Screening (Visit 1a).

Missing data will be handled by multiple imputation using an ANCOVA with factors of treatment, stratification factors and sex with age, time on treatment (date of last dose – date of first dose + 1), and baseline as covariates.

In order to reduce the variability in the time of post-baseline MRI acquisition, elapsed time from baseline to post-baseline MRI will be treated as a continuous variable, expressed as years from date of baseline MRI acquisition to date of off-treatment MRI acquisition visit (date of MRI visit – date of Baseline MRI + 1,). In addition, in order to reduce heterogeneity in variance and achieve linearity over time, log10 transformation will be applied to the htTKV data.

An ANCOVA will be used to analyze the change from baseline in log-transformed htTKV data on the PEAS to estimate annualized percent change in htTKV by time. The model will include fixed effects for the randomization stratification factors (CKD stage [CKD2 versus CKD3/4] and Mayo Clinic ADPKD Image Classification [1C, 1D, or 1E]) with baseline htTKV, and treatment group-by-time interaction as a covariate.

Example SAS code is shown below (treatment group is coded as 0=placebo and 1=lixivaptan):

PROC GLM ALPHA=0.01;

CLASS TREATMENT CKD_STAGE MAYO_CLASS;

MODEL CHG_LOGTKV = LOG_BASETKV TIME*TREATMENT CKD_STAGE MAYO_CLASS / SOLUTION SS3 CLPARM;

ESTIMATE "Annualized Change from Baseline for Lixivaptan (Log-scale)" INTERCEPT 1 LOG_BASETKV mean TIME*TREATMENT 0 1 CKD_STAGE 0.5 0.5 MAYO_CLASS 0.3333 0.3333 0.3333;

ESTIMATE "Annualized Change from Baseline for Placebo (Log-scale)" INTERCEPT 1 LOG_BASETKV mean TIME*TREATMENT 1 0 CKD_STAGE 0.5 0.5 MAYO_CLASS 0.3333 0.3333 0.3333;

ESTIMATE "Treatment Difference in Annualized Change from Baseline (Log-scale)" TIME*TREATMENT -1 1;

RUN;

Where "mean" is the overall mean of log-transformed baseline htTKV values.

A significance level of 0.01 (two-sided) will be used to declare statistical significance of treatment effect at the final analysis. Antilog (with a base of 10) of the treatment effect and 99% confidence intervals (99% CIs) derived from the model (in a log10 scale) provide a ratio of geometric means of the relative change (ratio) from baseline in htTKV (i.e., 100% plus annualized percent change).

8.3.2.1. Sensitivity Analysis of Annualized Percent Change from Baseline in htTKV

Two sensitivity analyses will be performed on the annualized percent change from baseline in htTKV using the PPAS and SEAS.

The sensitivity analysis using the PPAS is the same as the primary analysis for the annualized percent change from baseline in htTKV (Section 8.3.2) but using PPAS.

The sensitivity analysis will be performed for the annualized percent change from baseline to off-treatment follow-up Visit 25 after Week 52 in htTKV using the SEAS. Missing data will be

handled by multiple imputation using an ANCOVA with factors of treatment, stratification factors and sex with age, time on treatment (date of last dose – date of first dose + 1), and baseline as covariates. An ANCOVA model with fixed effects of treatment (0=placebo, 1=lixivaptan) and randomization stratification factors, and baseline, (elapsed) time, treatment-by-time as a covariate will be used to fit the log10-transformed htTKV data.

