8.1 Sample Size

Part 1:

Based on the results of the REPRISE trial with tolvaptan, (Torres et al, 2017) it is assumed that the standard deviation for the primary efficacy endpoint, change from baseline to post-treatment follow-up in mean eGFR, is 6.20 mL per minute per 1.73 m². Assuming a between-treatment group difference of -1.40 mL per minute per 1.73 m² and a randomization ratio of 2:1 for lixivaptan to placebo, a sample size estimate of 1314 participants (438 placebo-treated participants and 876 lixivaptan-treated participants) is required to achieve 90% power at a significance level of 0.01. In order to compensate for possible dropouts, this estimate has been adjusted up to 1350 participants (450 placebo participants and 900 lixivaptan participants). It is estimated that approximately 2250 participants will need to be screened in order to randomize 1350 participants.

A blinded sample size re-estimation (BSSR) to estimate the variance corresponding to the primary efficacy estimand is planned after at least 20% of the total randomized participants have completed Part 1 of the study or before screening for the study has ended (Section 8.2).

Part 2:

This is a convenience sample based on the number of participants who elect to continue into Part 2. It is estimated that approximately 1350 participants will be randomized in Part 1. All participants except those who discontinue due to an adverse event or withdraw consent will continue into Part 2. Approximately 90% (1215) of Part 1 participants are anticipated to continue into Part 2.

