8.6.2. Annualized Percent Change in Height-adjusted Liver Volume (htLV)

This analysis is based on the annualized percent change in htLV from baseline to 28 days after the last dose of the study drug, i.e., Visit 25 during the Follow-up Period I after Week 52 for ontreatment completers or, for participants who discontinue study drug treatment prior to Week 52 [Visit 22], during the Follow-up Period 28 days following study drug treatment discontinuation. Baseline htLV is the one obtained at Screening (Visit 1a). Missing data will not be imputed for this analysis.

In order to reduce the variability in the time of post-baseline MRI acquisition, elapsed time from baseline to post-baseline MRI will be treated as a continuous variable, expressed as years from date of Baseline MRI acquisition to date of MRI acquisition visit (date of MRI visit – date of Baseline MRI + 1). In addition, in order to reduce heterogeneity in variance and achieve linearity over time, log10 transformation will be applied to the htLV data.

An ANCOVA will be used to analyze the log-transformed htLV data on the PEAS to estimate annualized percent change in htLV by time. The model will include fixed effects for treatment group (0=placebo, 1=lixivaptan), the randomization stratification factors (CKD stage [CKD2 versus CKD3/4] and Mayo Clinic ADPKD Image Classification [1C, 1D, or 1E]), baseline htLV, (elapsed) time, and treatment group-by-time interaction as a covariate.

Example SAS code in Section 8.3.2 for the htTKV analysis can be used to analyze the htLV when the log-transformed htTKV data are replaced by the log-transformed htLV data.

A significance level of 0.01 (two-sided) will be used to declare statistical significance of treatment effect at the final analysis. Antilog (with a base of 10) of the treatment effect and 99% confidence intervals (99% CIs) derived from the model (in a log10 scale) provide a ratio of geometric means of the relative change (ratio) from baseline in htLV (i.e., 100% plus annualized percent change).

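### The htTKV Week 52 sensitivity model adds a treatment main effect that leaves the annualised contrast resting on scan-date spread; the htLV text lists the same terms but its code omits them

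*SAP*

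**What the plan says.** Three SAP passages bear on this.

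- **8.3.2, main htTKV analysis.** The code is "MODEL CHG_LOGTKV = LOG_BASETKV TIME*TREATMENT CKD_STAGE MAYO_CLASS". All participants share one intercept, and there is no treatment or time main effect. The annualised treatment difference is the contrast `TIME*TREATMENT -1 1`. The section adds: "A significance level of 0.01 (two-sided) will be used to declare statistical significance of" the treatment effect.
- **8.3.2.1, sensitivity analysis on the SEAS.** The target is the scan at Visit 25 after Week 52, with missing data multiply imputed. The model has treatment and the stratification factors as fixed effects, "and baseline, (elapsed) time, treatment-by-time as a covariate will be used to fit the log10-transformed htTKV data". No code and no contrast are given.
- **8.6.2, htLV (exploratory).** "The model will include fixed effects for treatment group (0=placebo, 1=lixivaptan"), and the list goes on to strata, baseline, elapsed time and group-by-time. The section then says the 8.3.2 code may be reused with htLV data, and that code has neither main effect. Missing scans are not imputed. Participants who stop early are scanned 28 days after stopping.

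**The concern.** There is one post-baseline scan per participant. In the 8.3.2 model the common intercept acts as an anchor, so each arm's change divided by its elapsed time is well estimated. Once each arm has its own intercept, the treatment-by-time coefficient becomes the difference between two within-arm slopes of change on scan date. If everyone is scanned at nearly the same time, those slopes are scarcely identified.

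At stake is the only planned analysis that takes htTKV to Visit 25 after Week 52 regardless of early discontinuation. It is meant to test the robustness of the second endpoint in the type I error hierarchy (SAP 6.1.3). For htLV the issue is that text and code define different models, one of which is uninformative.

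**Working it through.** **The plan's own figure.** The documents state no standard error, power or sample size for htTKV or htLV. The design figure that can be checked is the eGFR sample size in Protocol 8.1: "a sample size estimate of 1314 participants (438 placebo-treated participants and 876 lixivaptan-treated participants) is required to achieve 90% power". Its inputs are a difference of -1.40, a standard deviation of 6.20 and "a randomization ratio of 2:1 for lixivaptan to placebo". Placebo n = (1 + 1/2) × (6.20/1.40)² × (2.576 + 1.282)² = 1.5 × 19.61 × 14.88 ≈ 438, and 3 × 438 = 1314. It reproduces at two-sided 0.01. Below, N is the planned 450 + 900.

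**Elapsed time at Visit 25 after Week 52 (days).** No section gives its spread, so it is built from the protocol windows, each taken as uniform.

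| Component | Source | Mean | Variance |
|---|---|---|---|
| Baseline MRI to Visit 2 | Protocol 6.1, about 1 week; assumed fixed 7, or 7–28, or 7–49 | 7; 17.5; 28 | 0; 21²/12 = 36.75; 42²/12 = 147 |
| Visit 2 to Visit 3 | Protocol Table 3, 7 ± 2 | 7 | 4²/12 = 1.33 |
| Titration | Protocol 6.3, 35 or 42; equal split assumed | 38.5 | 3.5² = 12.25 |
| Double-blind treatment | Protocol Table 3, 364 ± 5 | 364 | 10²/12 = 8.33 |
| Last dose to MRI | Protocol Table 3, 25–31 | 28 | 6²/12 = 3 |
| Added day in the SAP formula | SAP 8.3.2 | 1 | 0 |

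The totals are means of 445.5, 456 and 466.5 days (1.22, 1.25 and 1.28 years), with variances 24.9, 61.7 and 171.9, so SDs of 5.0, 7.9 and 13.1 days. Protocol 6.4.2 gives ± 3 rather than ± 5 days for Visit 22, which would narrow the spread further.

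**Standard error of `TIME*TREATMENT -1 1`.** With residual SD σ, mean time t and SD of time s:

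- 8.3.2 model: about σ√(1/450 + 1/900)/t = 0.0577σ/t.
- With a treatment main effect: about 0.0577σ/s.
- Ratio: about √(1 + (t/s)²).

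| MRI-to-Visit 2 gap | t/s | Ratio from the design matrix, dates simulated |
|---|---|---|
| 7 days | 445.5/4.99 = 89 | 89 |
| 7–28 days | 456/7.85 = 58 | 59 |
| 7–49 days | 466.5/13.11 = 36 | 36 |

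**Which term causes it.** Adding time alone to the 8.3.2 model gives a ratio of 1.00, because time is the sum of the two arm-specific time columns. Adding treatment alone, or treatment and time, gives identical inflation.

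**Other contrasts from the same model.** The treatment coefficient alone is the arm difference extrapolated to time zero. Relative to a plain treatment comparison, its standard error is inflated by the same factor. The fitted difference at 1 year has a ratio of 10 to 20. The treatment difference at the mean scan time, divided by that time, has a ratio of 1.00.

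**htLV, if the 8.6.2 text is followed.** Early stoppers spread the scan times. With stopping days assumed uniform over the year:

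| Stopping early | Ratio |
|---|---|
| 1% | 20–24 |
| 2.7% (36/1350, the dropout allowance) | 13–14 |
| 5% | about 10 |
| 10% (the protocol's 90% completion) | about 7 (mostly 6 to 8 in single simulated trials) |

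**Power.** Take an effect that has 90% power under the 8.3.2 model, so a standardised effect of 2.576 + 1.282 = 3.858. At ratio 7, 3.858/7 = 0.551 and power is Φ(0.551 − 2.576) + Φ(−0.551 − 2.576) = 0.0214 + 0.0009, about 2%. At ratio 36 it is about 1.0%, the size of the test.

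**The case against.** The strongest reply is that 8.3.2.1 names no contrast. An analyst could report the difference at the mean scan time divided by that time and lose almost nothing (ratio 1.00 to 1.01). That is correct, and it is why the inflation is conditional on reading the effect as in 8.3.2. But 8.3.2 supplies the only annualised htTKV contrast in the SAP, the other single-coefficient reading is equally inflated, and nothing directs the analyst to the combined contrast.

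For htLV, a programmer who uses the cited code gets the 8.3.2 model and no inflation. This also stands: the htLV defect is a conflict between text and code. A reader might infer that the htLV test has no power as planned, or that htLV scans also fall at nearly one elapsed time. The documents support neither. The code is sound, and early stoppers are scanned early.

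A reader might also blame both added main effects. Only treatment matters.

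Finally, the consequences are limited. The PPAS sensitivity analysis repeats the 8.3.2 model and stays interpretable. htLV is exploratory and outside the hierarchy. SAP 12 records that the study ended with five participants randomised and that no statistical analyses will be run. All of that stands, so the point concerns the plan as written.

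**Conclusion.** The point holds in a bounded form. Read with the 8.3.2 contrast, the 8.3.2.1 model gives a standard error roughly 35 to 90 times that of the main model. This rests on uniform protocol windows, an equal split of titration lengths, an MRI-to-Visit 2 gap of 7 days up to a range of 7–49 days, and every analysed scan, observed or imputed, falling at Visit 25 after Week 52. Such an analysis is uninformative about the main htTKV result in either direction. For htLV the factor is about 7 (up to about 8) at 10% early stopping with uniform stopping times, and larger with fewer early stoppers, but only if the text overrides the code.

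Two stronger inferences fail. The sensitivity result would not contradict the main one: a very wide interval is compatible with it, although it could be misread as lack of robustness. Nor is the standard error miscalculated: it is right for a within-arm slope difference, which is not the annualised effect of interest. The gated test in 8.3.2 is unaffected.

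**What to change.** In SAP 8.3.2.1 and 8.6.2, delete the treatment main effect, and with it the redundant time term, so that both sections use the 8.3.2 model and contrast. Make the 8.6.2 text match its code. This returns the ratio to 1.00.

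Alternatively, keep the richer model and state the contrast as the treatment difference at the mean scan time divided by that time (ratio 1.00 to 1.01, including with 10% early stopping).

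Dividing each participant's log change by elapsed years should not be offered as equivalent, because it up-weights early scans. A participant stopping on day 1 would be scanned at about 7 + 7 + 38.5 + 1 + 28 + 1 = 82.5 days, a multiplier of 365.25/82.5 = 4.4. With 10% early stopping and constant residual SD, its standard error was about 16% larger than that of the 8.3.2 model. SAP 8.2 restricts such annualisation outliers for eGFR, but no such restriction covers htLV.

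The cost is a few lines of SAP wording. No data collection or sample size changes.

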8.4. Subgroup Efficacy Analysis (Part 1)

Descriptive statistics will be presented for the primary and secondary efficacy analyses for the following subgroups:

- Age (Tertiles)
- Sex (Male, Female)
- Race (White, non-White)
- Region (US, non-US)
- Baseline eGFR (*≤*median, *>*median)
- CKD stage (CKD2, CKD3/4)
- Mayo Clinic ADPKD Image Classification (1C, 1D, and 1E)
- Baseline htTKV (*≤*median, *>*median)

8.5. Health Outcomes Analyses (Part 1)

The endpoints from ADPKD-Impact Scale (ADPKD-IS), ADPKD-Pain and Impact Scale (ADPKD-PDS), ADPKD-Urinary Impact Scale (ADPKD-UIS) Patient Reported Outcomes (PROs) will be evaluated separately by domain (see Section 4.1.2.2) for the PEAS. Missing data are not imputed prior to the analysis.

An analysis utilizing a MMRM will be performed on the changes in each domain score from baseline (visit 2) to all Double-Blind, Randomized Treatment Period visits up to Follow up Period I (i.e., Visits 12, 15, 18, 22 and 25). The MMRM will include treatment group, visit, treatment group-by-visit, and randomization stratification factors (CKD stage [CKD2 versus CKD3/4] and Mayo Clinic ADPKD Image Classification [1C, 1D, or 1E]) as fixed effects, baseline as a covariate, and the baseline-by-visit interaction. An unstructured variance-covariance matrix is assumed for the repeated measures. The treatment difference in change from baseline at each post-baseline visit will be produced from the analysis.

Example SAS code is shown below:

```
PROC MIXED EMPIRICAL ALPHA=0.01;

CLASS TREATMENT VISIT CKD_STAGE MAYO_CLASS USUBJID;

MODEL CHANGE = TREATMENT BASELINE VISIT VISIT*TREATMENT BASELINE*VISIT CKD_STAGE

MAYO_CLASS /SOLUTION CL;

REPEATED VISIT/TYPE=UN SUB= USUBJID;

LSMEANS VISIT*TREATMENT/ALPHA=0.01 PDIFF CL;

ESTIMATE 'Lixivaptan – Placebo Change from Baseline at Visit 12'

TREATMENT -1 1 VISIT*TREATMENT -1 0 0 0 0 1 0 0 0 0;
```

ESTIMATE 'Lixivaptan – Placebo Change from Baseline at Visit 15' TREATMENT -1 1 VISIT*TREATMENT 0 -1 0 0 0 0 1 0 0 0;

RUN;

...

In addition, descriptive summary (n, mean, standard deviation, median, minimum, and maximum) will be used to summarize the change from baseline in each domain score at the Lixivaptan Titration Period visits (Visits 4-9) for all the participants in the Lixivaptan Treated Safety Set.

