8.3 Populations for Analysis

Part 1:

The following populations will be used for analyzing the data from Part 1:

Treated Safety Set: The Treated Safety Set consists of all participants who received at least 1 dose of study drug in Part 1.

Randomized Safety Set: The Randomized Safety Set consists of all participants in the Treated Safety Set who are randomized and receive at least 1 dose of randomized study drug.

Primary Efficacy Analysis Set (PEAS): The PEAS consists of all participants in the Randomized Safety Set who have both baseline and at least 1 valid assessment of eGFR in the Follow-up Period.

Secondary Efficacy Analysis Set (SEAS): The SEAS consists of all participants in the Randomized Safety Set who have both baseline and at least 1 on-treatment assessment of eGFR.

Part 2:

The following populations will be used for analyzing the data from Part 2:

Long-term Safety Set: The Long-term Safety Set consists of all participants in the Randomized Safety Set of Part 1 who receive at least 1 dose of lixivaptan during Part 2.

Long-term Full Analysis Set: The Long-term Full Analysis Set consists of all participants in the Long-term Safety Set who have at least 1 on-treatment measurement of eGFR in Part 2.

Long-term Efficacy Analysis Set: The Long-term Efficacy Analysis Set consists of all participants in the Long-term Full Analysis Set who were randomized to lixivaptan in Part 1.

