8.10.2 Urinary Osmolality

Descriptive statistics for the change from baseline in morning spot urine osmolality will be presented by treatment group for the Treated Safety Set in Part 1 and overall, for the Long-term Safety Analysis Set in Part 2 at each scheduled time point. The number (%) of participants who show suppressed urine osmolality in each treatment group, defined by 2 levels of spot urine osmolality – ≤ 250 mOsm/kg and ≤ 300 mOsm/kg – will be summarized descriptively at each time point.

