4.2.3.1. Exploratory Endpoints

- The annualized percent change in htLV determined by MRI from baseline (posttreatment follow-up visit [Visit 25] after Week 52 in Part 1) to post-treatment follow-up during Follow-up Period II after Week 104 for on-treatment completers, or, for participants who discontinue study drug treatment prior to Week 104 [Visit 42], during the Follow-up Period 28 days following study drug treatment discontinuation in Part 2;
- Mean change from baseline in morning spot urine osmolality in Part 2; Baseline is defined as urine osmolality obtained at 28 days post-treatment follow-up visit (Visit 25) after Week 52 in Part 1.
- The annualized change in eGFR calculated from the 2021 CKD-EPIcr-cys_R equation from baseline to the post-treatment follow-up. The definitions of baseline eGFR, post-treatment follow-up eGFR and annualization are the same as the key comparison endpoint in Part 2 (Section 4.2.1.1) except for using the different eGFR equations.

5. Analysis Populations

The following analysis populations are planned for this study:

Part 1:

- **Placebo Run-in Safety Set:** The Placebo Run-in Safety Set includes all participants who received at least one dose of placebo during Placebo Run-In Period in Part 1.
- Lixivaptan Titration Safety Set: The Lixivaptan Titration Safety Set includes all participants who received at least one dose of lixivaptan during Lixivaptan Titration Period in Part 1.
- **Randomized Safety Set:** The Randomized Safety Set includes all participants who received at least one dose of study drug after randomization.
- Intent-to-Treat Analysis Set (ITT): The ITT includes all participants who were randomized in Part 1.

- **Modified Intent-to-Treat Analysis Set (mITT):** The mITT includes all participants in the ITT who received at least one dose of study drug in Part 1. Note that the mITT Analysis Set consists of the same set of the participants in the Randomized Safety Set.
- **Primary Efficacy Analysis Set (PEAS):** The PEAS includes all participants in the mITT Analysis Set who have both baseline and at least one assessment of eGFR after the treatment is complete or discontinued in Part 1.
- Secondary Efficacy Analysis Set (SEAS): The SEAS includes all participants in the mITT Analysis Set who have both baseline and at least one on-treatment assessment of eGFR.

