8.6.3. Urine Osmolality

Descriptive statistics for the change from baseline (Visit 2) in morning spot urine osmolality will be presented by treatment group for the PEAS. The number (%) of participants who show suppressed urine osmolality in each treatment group, defined by 2 levels of spot urine osmolality \leq 250 mOsm/kg and \leq 300 mOsm/kg will be summarized descriptively at each time point.

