8.10. Health Outcome Analyses (Part 2)

The descriptive statistics for change from baseline in each domain score of three patient reported health questionnaires are presented at each evaluated visit in Part 2 by treatment cohort and overall for all the participants in the P2EAS. Baseline score is defined as the domain score from Follow-up period I (Visit 25) after Week 52 in Part 1. In order to compare the results from Part 2 to those in Part 1, the descriptive statistics for change from baseline in each domain score of three patient reported health questionnaires are presented at each corresponding visit at Part 1 by treatment cohort.

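### SAP 8.5 runs the patient-reported outcome model on the PEAS, so dosed participants with no eGFR after treatment lose questionnaire scores the model could use

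*SAP*

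**What the plan says.** **Part 1 questionnaires.** SAP 8.5 models change in each domain score at Visits 12, 15, 18, 22 and 25 by MMRM, imputes nothing, and states that the endpoints "will be evaluated separately by domain (see Section 4.1.2.2) for the PEAS". Protocol 8.9.2 names no analysis set and leaves the detail to the SAP.

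**The PEAS.** SAP 5 limits it to mITT participants "who have both baseline and at least one assessment of eGFR after the treatment is complete or discontinued in Part 1". Protocol 8.3 asks that they "have both baseline and at least 1 valid assessment of eGFR in the Follow-up Period".

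**The wider set.** SAP 5 already defines one: "The mITT includes all participants in the ITT who received at least one dose of study drug in Part 1". It adds that these are the same people as the Randomized Safety Set.

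**Part 2 questionnaires.** SAP 8.10 summarises them "by treatment cohort and overall for all the participants in the P2EAS". The P2EAS (SAP 5) needs an off-treatment eGFR in Part 2.

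**Urine osmolality, Part 1.** SAP 8.6.3 says the summary "will be presented by treatment group for the PEAS". Protocol 8.10.2 says it "will be presented by treatment group for the Treated Safety Set in Part 1". SAP 15 lists the redefined Part 2 sets but not this change.

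**The concern.** The scores at Visits 12, 15, 18 and 22 are collected while participants are on treatment. Whether someone later gives a creatinine sample after stopping is a post-randomisation event unrelated to those scores. The PRO objective (Protocol 2.1.1, SAP 2.1.5) concerns participants treated with each drug, which is the mITT.

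The restriction also works against the chosen method. SAP 6.1.4 describes the MMRM as the modelling approach under missing at random. Its merit is that it uses the visits a participant attended before leaving. The PEAS deletes those records, including visits that were fully observed. The primary endpoint has mITT, MAR, MNAR and tipping-point sensitivity analyses (SAP 8.2.1.1), but the PROs have none on a wider set.

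The UIS is where this could matter. It measures frequency, urgency and nocturia, and Protocol 1.9 names increased urine output as a leading adverse effect. Participants who leave without any follow-up blood may include those most bothered.

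**Working it through.** **1. How many participants the plan allows to be lost.** Protocol 8.1 gives SD 6.20, difference 1.40, 2:1 allocation, alpha 0.01 and 90% power. Taking alpha as two-sided:

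placebo n = (1 + 1/2) × (2.576 + 1.282)² × (6.20/1.40)² = 437.7, rounded up to 438; total 3 × 438 = 1314.

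This reproduces the stated 1314; a one-sided test would give 1149. The increase to 1350 for dropouts allows 36/1350 = 2.7%. Since the primary analysis runs on the PEAS, this is the plan's nearest figure for PEAS exclusions. Protocol 8.1 also expects 1350 − 1215 = 135 (10%) not to enter Part 2. That is a ceiling, because many of these people would still give follow-up blood.

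**2. Bias formula.** Let d be the share of an arm excluded and g the mean score change of excluded minus retained participants (positive means worse). Then

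PEAS difference − full difference = −(dL × gL − dP × gP).

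The UIS difference is understated only if dL × gL exceeds dP × gP. The documents give none of these four quantities.

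**3. Illustration with assumed scores.** Suppose UIS worsens by 0.9 in retained and 2.0 in excluded lixivaptan participants (gL = 1.1), that placebo does not change, and that every excluded person was scored at Visit 12. The PEAS then shows 0.90.

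| Lixivaptan excluded | Full difference | Understated by |
|---|---|---|
| 2.7% | 0.973 × 0.9 + 0.027 × 2.0 = 0.930 | 0.03 (3%) |
| 10% | 0.90 × 0.9 + 0.10 × 2.0 = 1.01 | 0.11 (11%) |

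**4. Other assumptions.** With 2.7% excluded in each arm:
- excluded participants no different, or equally worse in both arms: bias 0;
- only lixivaptan exclusions 0.5 worse: −0.027 × 0.5 = −0.014;
- only placebo exclusions 0.5 worse: +0.014.

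**5. Likelihood-based check.** A simulation compared mITT with PEAS estimates from a monotone-missing likelihood model (900 and 450 participants, four on-treatment visits, assumed true difference 0.5, SD 1, correlation 0.6). Dropout depended on the last observed score, and 27%, 50% or 100% of dropouts gave no follow-up blood.

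| Dropout related to score | Dropout, lixivaptan / placebo | PEAS/mITT ratio at Visit 22 |
|---|---|---|
| Not at all | about 8% / 8% | 1.00 |
| Moderately | about 11% / 9% | 0.987 to 0.998 |
| Strongly | about 17% / 11% | 0.935 to 0.987 |

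The lowest ratio needs strong dependence and no dropout giving follow-up blood; at Visit 12 the same case gives 0.920. The mITT estimate stayed between 0.495 and 0.505 throughout, as expected when data are missing at random.

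**6. Precision.** If the lost records were complete and lost equally by arm, the standard error would rise by 1/√0.973 − 1 = 1.4% at 2.7% excluded, and by 1/√0.90 − 1 = 5.4% at 10%. Partial records would cost less.

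**The case against.** A reader might infer that the urinary-burden difference is understated as a matter of fact. The documents do not support that. They do not say how many dosed participants would miss the PEAS, from which arm, or with what scores. That exclusions would be mostly lixivaptan by count is no evidence, since 2:1 allocation produces that by itself.

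The excluded group should also be small:
- Participants take lixivaptan for 5 to 6 weeks before randomisation and are asked whether they would stay on it for 24 months. Those who cannot tolerate the minimum dose are not randomised (Protocol 5.2).
- Every randomised participant who stops drug is meant to give three follow-up creatinine samples unless consent for data collection is withdrawn (Protocol 4.2.4). Protocol Appendix 5 offers alternatives before withdrawal.
- The early termination visit collects questionnaires and creatinine together (Protocol 6.4.2). Read literally, the SAP's PEAS wording could be met by that sample; the protocol's Follow-up Period wording could not.

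Urinary tolerability is also visible elsewhere. Aquaretic problems are recorded as adverse events (Protocol 7.3.8.2), and safety is analysed on the Randomized Safety Set (SAP 9). The PROs sit outside the testing hierarchy (SAP 6.1.3).

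These points stand against any claim of a known or large bias. They do not justify the set. The people still excluded are mainly those who withdrew consent or were lost, whose scores are most likely to be informative, and adverse event tables do not replace the randomised UIS comparison.

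The bias argument should not be stretched to osmolality or Part 2. Osmolality is a descriptive laboratory summary. Part 2 puts everyone on lixivaptan, so there is no concurrent placebo difference to understate. Protocol 8.14 lets the SAP modify planned analyses, and the Treated Safety Set includes people never randomised, so it does not divide cleanly by treatment group. What remains for osmolality is an unlisted change.

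**Conclusion.** The concern holds as a poor choice of analysis set. The PRO model discards on-treatment scores because of a later, unrelated blood sample, and nothing in the plan shows whether that matters. Some precision is lost and the comparison can be biased. The direction is not established. Understatement of the UIS difference requires exclusions that are more frequent or more burdened on lixivaptan. The 0.03-point and 0.11-point figures rest on the assumed scores in step 3 and on using 2.7% and 10% as stand-ins for PEAS exclusion.

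For osmolality the point is consistency with the protocol only. For Part 2 it is the same unnecessary condition on descriptive tables. No reported result is affected: SAP 12 records that the trial stopped with 5 participants randomised and that no statistical analyses will be performed. This is a correction to the plan.

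**What to change.** - **SAP 8.5:** fit the same MMRM in all mITT participants with a baseline and at least one post-baseline score for the instrument. Keep the PEAS version as a supportive table.
- **SAP 8.10:** base the descriptive summaries on P2SS participants with a Part 2 baseline and a Part 2 score.
- **SAP 8.6.3 and 15:** summarise osmolality by treatment group in Randomized Safety Set (mITT) participants with a baseline and a post-baseline value. List the departure from the protocol's Treated Safety Set in SAP 15.
- **SAP 5 and Protocol 8.3:** reconcile the two PEAS definitions, stating whether a creatinine drawn at the early termination visit after the last dose qualifies.

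The cost is SAP wording, a population flag and one extra table per instrument. No new data are needed.
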